2. OBJECTIVES

This trial will assess the safety, tolerability and efficacy of a treat and extend management protocol for DME. Patients will be enrolled into one of three treatment groups: (1) monthly intravitreal injections of 0.3 mg ranibizumab (Monthly Cohort, 30 eyes); (2) monthly intravitreal injections of 0.3 mg ranibizumab for 4 visits, followed by a “Treat and EXtend” protocol based on pre-specified criteria of disease activity (T-REX cohort, 60 eyes); (3) monthly intravitreal injections of 0.3 mg ranibizumab for 4 visits combined with adjunctive Guided focal Laser macular photocoagulation to microaneurysms at week 4 and then every 3 months if leakage is present on fluorescein angiography, followed by a treat and extend protocol based on pre-specified criteria of disease activity (GILA cohort, 60 eyes).

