2.2 Secondary Objectives

- Incidence and severity of adverse events (ocular and non-ocular).
- Total number of intravitreal injections required during each year of the study period (week 52, week 104, and week 156). In a separate proof of concept analysis, the number of intravitreal injections in the TREX and GILA cohorts over the 36-month study period will be compared with that of the other two cohorts ($p = 0.20$).
- Total number of office visits and imaging studies performed during each year of the study period.
- Mean change in central foveal thickness per SD-OCT from randomization to 12 months (week 46 – week 57), randomization to 24 months (week 92 – week 107), and randomization to 36 months (week 156).
- Percentage of eyes gaining or losing 3 lines of vision or more and 1 line of vision or more at 6 months (week 22 – week 29), 12 months (week 46 – week

57), 18 months (week 70 – week 85), 24 months (week 92 – week 107), and 36 months (week 156) from Day 0.

- Noninferiority comparison (margin of 9 letters) of mean change in ETDRS vision from Day 0 to 24 months (week 92 – week 107) between the three study groups.
- The percentage of eyes which show progression of proliferative diabetic retinopathy requiring panretinal photocoagulation and/or pars plana vitrectomy over the 36-month study period.
- The percentage of eyes in the TREX and GILA cohorts who are eligible to begin the extension phase after 4 treatment visits.
- For TREX and GILA Cohorts, the time to achieve a “Secondary or Tertiary Baseline” retinal thickness.
- Percentage of eyes in each cohort that have shown a two-step change (increase and decrease) in diabetic retinopathy at 24 months and 36 months from day 0.

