Subjects will be evaluated for focal laser treatment at week 116, week 128, week 140, and week 152. If the subject has received ≥ 2 intravitreal injections of ranibizumab within the prior 90 day period, then fluorescein angiography will be performed and focal laser treatment will be applied to any leaking microaneurysms. If the patient does not meet this criteria for focal laser treatment, then fluorescein angiography and focal laser treatment will be deferred and reassessed at the subsequent laser evaluation visit. Focal laser treatment and focal laser re-treatment will be administered no more than once every 90 days.

Focal laser therapy will be applied to all leaking microaneurysms on fluorescein angiography. Focal laser therapy will not be applied if significant macular ischemia is present involving the foveal avascular zone (once this has been determined additional fluorescein angiography and focal laser treatment planning should not be performed as the subject will no longer be eligible for focal laser treatment). Focal laser will also not be applied if treatment is considered too close to the foveal avascular zone or to macular edema not related to DME (cystoid macular edema, etc.). If no microaneurysms are present on fluorescein angiography, then focal laser therapy should be deferred and reassessed with repeat fluorescein angiography at the first visit that occurs after 90 days.

2. TREX Cohort (60 eyes): Monthly intravitreal injections of 0.3 mg ranibizumab for four (4) visits. If the central foveal thickness is ≤ 325 μm at the fourth visit (Week 12) then the baseline retinal thickness will be recorded, the eye will receive 0.3 mg ranibizumab and the study eye will begin the extension phase of the study. For all subsequent visits in the extension phase, appropriate changes to the treatment interval with 0.3 mg ranibizumab (i.e. extend, maintain, reduce) will be made based on pre-specified SD-OCT criteria (SEE TREATMENT INTERVAL DETERMINATION). Treatment is rendered at

every visit, no earlier than 7 days before the target date and no later than 7 days after the target date, but the time between visits is individualized based on each subject's response to treatment. Dosing should not occur earlier than 21 days after previous treatments.

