3. GILA Cohort (60 eyes): Monthly intravitreal injections of 0.3 mg ranibizumab for four visits combined with Guided LAser (GILA) photocoagulation to all microaneurysms in the area of DME at the second visit (Week 4). Fluorescein angiography is to be repeated approximately every 3 months (the first visit that occurs ≥ 90 days from the preceding fluorescein angiography visit). Guided laser will be repeated at those visits if leakage is present from microaneurysms.

If the central foveal thickness is $\leq 325 \mu\text{m}$ at Week 12 then the baseline retinal thickness will be recorded, the eye will receive 0.3 mg ranibizumab, and the study eye will begin the extension phase of the study. In the extension phase, appropriate changes to the treatment interval with 0.3 mg ranibizumab (i.e. extend, maintain, reduce) will be made based on pre-specified SD-OCT criteria (SEE TREATMENT INTERVAL DETERMINATION). Treatment is rendered at every visit, no earlier than 7 days before the target date and no later than 7 days after the target date, but the time between visits is individualized based on each subject's response to treatment. Dosing should not occur earlier than 21 days after previous treatments.

If the central foveal thickness is $> 325 \mu\text{m}$ at week 12, then the patient will continue to receive monthly intravitreal injections of 0.3 mg ranibizumab and possible guided laser photocoagulation, approximately every 3 months until the central foveal thickness is $\leq 325 \mu\text{m}$. Once the central foveal thickness is $\leq 325 \mu\text{m}$, then the study eye will begin the extension phase of the study.

Starting at week 104, study eyes will have the opportunity to undergo treatment on a pro re nata (PRN) basis. Thus, eyes who have a central subfield thickness (CST) ≤ 325 microns at the week 104 visit, will not be given treatment at week 104. Starting at week 104, eyes will be seen every 4 weeks and will be given an intravitreal injection of ranibizumab 0.3 mg only if the CST is > 325 microns. Eyes will also receive treatment if there is a > 5 letter loss due to DME (compared to the vision at week 104), regardless of thickness on OCT.

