If at any point in the study period, the study eye has improved more than 20% from the primary baseline thickness for three consecutive visits and there is less than 50 microns of variability in central foveal thickness between these visits, then a "Secondary Baseline" retinal thickness will be established. This "Secondary Baseline" retinal thickness will then be used for treatment interval determinations from that point forward. If the study eye has improved more than 20% from the secondary baseline thickness for three consecutive visits and there is less than 50 microns of variability in central foveal thickness between these visits, then a "Tertiary Baseline" retinal thickness will be established. This "Tertiary Baseline" retinal thickness will then be used for treatment interval determinations from that point forward.

Treatment Interval Determination For TREX and GILA Cohorts:

Starting at Week 12, if the central foveal thickness is $\leq 325 \mu\text{m}$, then the following re-treatment criteria will be applied at all visits. Eyes with central foveal thickness $> 325 \mu\text{m}$ at week 12 will continue to receive monthly injections of 0.3 mg ranibizumab until the central foveal thickness is $\leq 325 \mu\text{m}$, at which time the following re-treatment criteria will be applied at all visits. Eyes in the GILA cohort will continue to receive guided laser photocoagulation to microaneurysms every 3 months if leakage is present on fluorescein angiography. This treatment interval determination will continue up to week 104.

Extend Interval (by 2 weeks):

1. If the central foveal thickness on SD-OCT is within $\leq 10\%$ thicker or thinner compared to baseline (primary, secondary, or tertiary baseline) retinal thickness.

Maintain Interval:

1. If the central foveal thickness is between $> 10\%$ thicker and $\leq 20\%$ thicker from the baseline retinal thickness (primary, secondary or tertiary baseline) OR
2. If the central foveal thickness is $> 10\%$ thinner from baseline retinal thickness (primary, secondary or tertiary baseline).

Reduce Interval (by 2 weeks):

1. If the central foveal thickness is $> 20\%$ thicker from baseline retinal thickness (primary, secondary or tertiary baseline).

Reduce Interval to 4 weeks:

1. If there is a loss of more than 15 letters from best previous ETDRS vision, due to DME.

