4.8 STATISTICAL METHODS

4.8.1 Analysis of the Conduct of the Study

The analysis of complete data (36-month treatment period) for the study will be performed when all patients have either completed the visit at month 36 or discontinued early from the study, all data collected from the study are in the database, and the database is locked.

Interim analysis of data from the 12-month period will be performed when all patients have either completed the visit at month 12 or discontinued early from the study. Treatment assignment will be unmasked to the personnel performing the analysis when all data collected through month 12 are in the database and the data have been cleaned and verified. The Peto group sequential procedure ($Z \pm 3.0$ at all interim analyses) will be used to control for the possibility of type I error arising from the 12 month interim analysis.

For the primary objective, power calculations for different margins were undertaken. Familywise alpha of 0.05 was divided equally among three TOST (two one sided test) procedures ($\alpha=0.0167$): (1) comparing TREX vs. GILA in the 60 patients enrolled with bilateral disease, (2) TREX vs. control (total $n=90$, controls $n=30$), and (3) GILA vs. control (total $n=90$, controls $n=30$). A standard deviation of 11 letters was used for the power calculations and based from the RISE/RIDE data for subjects with DME. The power calculations suggests that the minimum boundary of equivalence for TREX vs. GILA that we can demonstrate is ± 7 letters (less than two lines of vision) and ± 9 letters (less than two lines of vision) for TREX and GILA vs. controls. Paired sample t-test will be used to compare TREX vs. GILA and two sample t-test will be used to compare the two groups vs. controls.

Because of the potential for confounding of the effect when comparing the control group (monthly cohort) to the TREX and GILA groups, we will use linear regression modeling with change in ETDRS as outcome

and cohort as main effect controlling for potential confounders (e.g., age, race, sex).

Adverse events, number of injections, and number of office visits will be approached statistically with descriptive analyses with point estimates and confidence limits provided. Exploratory linear, logistic, and time-to-event models will be used to analyze the other secondary outcomes.

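### Year 3 schedules laser evaluations 84 days apart but allows laser only every 90 days, so read literally it orders angiograms that cannot lead to laser

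*Combined protocol and SAP*

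**What the plan says.** Up to week 104, section 3.1 sets the timing of GILA angiography by days since the last one: "Fluorescein angiography is to be repeated approximately every 3 months (the first visit that occurs ≥ 90 days from the preceding fluorescein angiography visit"). Laser is tied to those same visits, so the two cannot fall out of step.

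The year-3 laser text works differently. It is repeated for the Monthly, TREX and GILA cohorts in both 3.1 and 4.2. It has five parts.

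- **Evaluation weeks:** "Subjects will be evaluated for focal laser treatment at week 116, week 128, week 140, and week 152".
- **Trigger:** if the eye has had at least two ranibizumab injections in the preceding 90 days, "then fluorescein angiography will be performed and focal laser treatment will be applied to any leaking microaneurysms".
- **Deferral:** an eye that fails this criterion has both angiography and laser put off to the next evaluation visit.
- **Laser limit:** treatment and re-treatment may be given at most once in 90 days.
- **Exceptions after angiography:** significant ischemia involving the foveal avascular zone ends both laser and further angiography. If no microaneurysms are seen, angiography is repeated at the first visit after 90 days.

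Section 4.5.1 adds that angiography guides focal laser at these four weeks when the laser criteria are met. Sections 2.2, 3.3.2 and 4.8.3 list a secondary outcome that depends on how many angiograms are done: "Total number of office visits and imaging studies performed during each year of the study period".

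**The concern.** The evaluation weeks and the laser limit do not fit together. Twelve weeks is less than 90 days, so an on-time evaluation that follows a laser at the previous one always falls inside the barred period. The angiography trigger looks only at injections. The deferral sentence refers to that same injection criterion, so it does not clearly cover an eye barred from laser because it was treated 84 days earlier.

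Two things are at stake. Patients may undergo an invasive dye test that cannot change their treatment at that visit. The year-3 imaging count also depends on how each site resolves the conflict.

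**Working it through.** The plan gives no figure of its own on this point, so the check is calendar arithmetic on its rules.

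**Inputs (3.1 and 4.2).** Evaluations at weeks 116, 128, 140 and 152; visits every 4 weeks from week 104; trigger of at least 2 injections in the prior 90 days; laser at most once per 90 days. A visit window of ±7 days is stated for the earlier treatment schedule, and I assume it also applies in year 3.

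**1. Spacing.** 128 − 116 = 12 weeks, and 12 × 7 = 84 days, which is less than 90. The same holds for 128 to 140 and for 140 to 152.

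**2. The trigger can be met inside the barred period.** The visits at weeks 116, 120 and 124 lie 84, 56 and 28 days before week 128. Injections at any two of them satisfy the criterion at week 128.

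**3. Worst case, nominal dates.** The eye meets the injection criterion and leaks at every evaluation, and had no laser in the 90 days before week 116.

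| Week | Days since last laser | Angiogram ordered | Laser allowed |
|---|---|---|---|
| 116 | more than 90, or none | yes | yes |
| 128 | 84 | yes | no |
| 140 | 168 | yes | yes |
| 152 | 84 | yes | no |

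Total: 4 angiograms and 2 lasers.

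**4. Do visit windows rescue it?** Let each evaluation slip independently by a whole number of days from −7 to +7, uniformly, around fixed target dates (an assumption). The gap is 84 + s2 − s1, and it reaches 90 when s2 − s1 ≥ 6. The number of such pairs is 9 + 8 + … + 1 = 45 out of 15 × 15 = 225, or 20%. If slips instead accumulate over the three visits between evaluations, the share is 813/3375 = 24%.

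For the worst-case eye with fixed targets, a third laser becomes possible with probability 0.20 + 0.80 × 0.20 = 0.36. Four lasers are never possible. At least one of the four angiograms is therefore futile in every case, and two are futile in 64% of cases.

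**5. The eye with no microaneurysms.** After a clear angiogram at week 116, the first visit more than 90 days later is week 132 (16 × 7 = 112 days). Week 128 is still a listed evaluation at 84 days. The text does not say which governs.

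**6. Effect on the imaging count.** Depending on the reading, the number of laser-evaluation angiograms in year 3 is:

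- 4 if the trigger is followed literally (weeks 116, 128, 140, 152);
- 2 if angiography is deferred with laser to the next listed evaluation (116, 140);
- 3 if it moves to the first visit after 90 days (116, 132, 148).

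**The case against.** The best defence is that the protocol already implies that an eye that cannot have laser should not have an angiogram. Section 4.5.1 makes year-3 angiography conditional on the laser criteria being met. The deferral sentence comes directly before the 90-day limit and puts off both procedures together. Eyes with foveal ischemia stop having angiograms precisely because they can no longer have laser. A sensible site could read the 90-day limit into the criteria. The week 108 to 156 schedule (Appendix A.1) is part of a flowchart supplied separately and not available here, and it may settle the matter.

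This shows that the likely intent agrees with the fix, and that ordering an angiogram is the literal reading rather than the only one. It does not remove the conflict. The only criterion the year-3 text names is the injection count, and the deferral sentence points back to that alone.

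It is also fair that 4 angiograms against 2 lasers is a worst case. The documents give no basis for estimating how many eyes would qualify and leak throughout.

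**Conclusion.** The point holds as a minor inconsistency in the year-3 text. An on-time eye lasered at one evaluation and still meeting the injection criterion is sent for an angiogram at the next, where laser is not allowed. The size is at most 2 avoidable angiograms per qualifying eye on nominal dates. Under the uniform-slip assumption only about 20% of consecutive evaluations reach 90 days. The wording is the same in all arms.

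A reader might infer three stronger criticisms, which the documents do not support.

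- **That the primary comparison is affected.** The 24-month window closes at week 107 and the first year-3 laser evaluation is at week 116. The TREX versus GILA statement ("minimum boundary of equivalence for TREX vs. GILA that we can demonstrate is ± 7 letters") is therefore untouched.
- **That the GILA laser schedule before week 104 is wrong.** Several places say "at week 4 and then every 3 months if leakage is present on fluorescein angiography" or similar without qualification, and the on-time gap is in fact at least 14 weeks, because target intervals are even numbers of weeks and 12 weeks is 84 days. But 3.1, 4.2 and 4.5.1 give an executable rule and call it approximate. Relabelling it, or aligning the strict inequality in 4.5.1 with 3.1, is optional wording.
- **That laser exposure will go unreported.** Laser sessions are in neither the outcome lists nor the descriptive list ("Adverse events, number of injections, and number of office visits will be approached statistically with descriptive analyses with point estimates and confidence limits provided"). Laser is protocol treatment, however, and 6.5 requires complete case report forms, so absence from those lists does not show that it goes unrecorded. A count by cohort would be a useful optional row.

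**What to change.** Keep the 90-day limit and the four evaluation weeks. In 3.1 and 4.2, for each cohort, add after the sentence that sets the limit:

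*If a listed evaluation falls fewer than 90 days after the last focal laser, both angiography and laser are deferred to the next listed evaluation. If the last angiogram showed no microaneurysms, the next one is done at the first visit more than 90 days later and not at an earlier listed evaluation.*

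The second sentence is needed because the first depends on the last laser and would miss an eye that had a clear angiogram and no laser. Check that Appendix A.1 says the same.

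On nominal dates the worst-case eye still has laser at weeks 116 and 140, and the angiograms at weeks 128 and 152 are dropped. The cost is wording in six places. Visits, sample size and the primary analysis do not change.

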3.2 Rationale For Study Design

Diabetic macular edema (DME) is the most common cause of severe vision loss in Americans under 60. However, even mild to moderate vision loss from DME is impactful, since it strikes individuals often in the productive periods of their lives. Until now, interventions for diabetic retinopathy have been focused on maintaining current visual function or slowing the rate of vision loss.

The RISE and RIDE studies were parallel, phase III, double-masked clinical trials designed to evaluate the efficacy and safety of ranibizumab in the treatment of DME. In similarly designed protocols, patients were treated with monthly injections of ranibizumab (0.3 mg and 0.5 mg) versus sham monthly injections (all arms could receive macular laser photocoagulation from month 3 if meeting predefined criteria). The 2-year results demonstrated a statistically significant benefit from ranibizumab across numerous parameters, including mean change in visual acuity, percent of 10 letter and 15 letter gainers, and reduction in retinal thickness by OCT. Other smaller clinical trials have also demonstrated superiority of ranibizumab to laser alone.

Rationale for “Treat and Extend” versus fixed dosing

RISE and RIDE employed fixed dosing strategies during the entire 3-year mandatory treatment period. Like age-related macular degeneration, the best data available suggests that no alternative to monthly dosing has been

identified. However, monthly dosing of ranibizumab is problematic in DME for several reasons. First, compliance is often difficult in this population. In the RISE and RIDE studies, and multiple DRCR.net protocols, dropout rates consistently approach 10% per year. In addition, the natural history of DME suggests that long-term treatment will be required. This is quite different from age-related macular degeneration and retinal vein occlusion, where the disease activity wanes over time in many patients.

Because of these and other realities, alternatives to chronic, monthly dosing need to be explored. The DRCR Network has employed a “4-2-7” strategy in which patients receive 4 mandatory doses, followed by PRN dosing based on clinical response. In this proposal, an initial loading dose of 4 injections is proposed because much of the vision gains in RISE and RIDE were attained during the first 120 days. By only extending the interval by 2 weeks at each successful visit, it is postulated that the gains achieved early on may be maintained without aggressive recurrence. Once a patient reaches an interval that limits the control of disease activity, their recurrence is likely to be mild or even subclinical. At one year, it is likely that there will be a wide variety of dosing intervals in the cohort, based on disease activity, addition of panretinal photocoagulation, or other factors. What is unknown is how the visual outcomes with a “treat and extend” protocol will compare to the RISE and RIDE trials.

Rationale for Guided Laser photocoagulation

Since the publication of the Early Treatment Diabetic Retinopathy Study (ETDRS), macular laser photocoagulation has been vital in the management of DME. Because of the retina community’s positive experience with macular laser, it is likely that many clinicians will utilize some form of combination therapy in clinical practice. Recent data published by the Diabetic Retinopathy Clinical Research Network’s (DRCR.net) protocol I offers some direction for inclusion of laser in this protocol. Although faithful treatment with ranibizumab alone offered the best final visual outcome, the number of injections required at long-term follow-up were less in patients that received macular laser sometime during their treatment. In Protocol I, patients who received deferred laser had better visual outcomes compared to those receiving laser at entry. It is felt that by treating initially with ranibizumab caused some resolution of the macular edema, which allowed for better treatment effect with lower laser power settings, thereby minimizing laser-induced scotomas.

A potential drawback of the modified-ETDRS focal laser protocol employed in most DME trials is that the laser application is guided manually, which can be difficult in a living, moving patient. Accuracy of treatment delivery is always a concern and collateral damage to the neurosensory retina can lead to vision loss in some patients. The navigated laser (NAVILAS) photocoagulator is a novel laser delivery system that utilizes a retinal eye-tracking and laser stabilization system (Kozak et al, 2012). It was designed to improve accuracy

and to provide the ability to localize microaneurysms, which may be difficult to target using a traditional slit-lamp laser. Several studies have shown that the NAVILAS system is safe and achieves a higher rate of accuracy in photocoagulation treatments than standard manual-technique methods (Kozak et al, 2012). Because the NAVILAS photocoagulator uses a camera-based system, larger areas of the retina can be visualized, there is less glare artifact, and the patient is more comfortable (Kernt et al, 2011). A further advantage of the NAVILAS system is that it allows standardized laser treatment to all microaneurysms in the area of DME, which would be beneficial for this study and future clinical trial designs.

Summary

To date, evidence from multiple clinical trials suggests that monthly ranibizumab combined with laser sometime during the beginning of therapy offers the best long-term clinical outcomes. Although a promising therapy, there are limitations to chronic monthly therapy. By exploring a treat and extend strategy once disease activity is under control, the investigators postulate that extending maintenance intervals can preserve the gains of initial monthly injections and reduce treatment burden.

